13.1.9.3. Responder Endpoints

In an efficacy analysis in which subjects are classified as either a responder or a non-responder (binary outcome) based on dichotomizing a continuous variable, any subject who does not provide an assessment at the specified timepoint for the defining of response will be considered to be a non-responder. That is, for the percentage of responders, the subject will be included in the denominator and will not contribute to the numerator.

For sensitivity analyses using only “observed cases,” subjects who do not provide an assessment at the specified timepoint for the defining of response will not be included. That is, for the percentage of responders, the subject will not be included in the numerator or the denominator.

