7.8. Criteria for Study Termination

The Sponsor reserves the right to terminate the study at any time. It is normal procedure to review the emerging clinical and safety data. As a result of such a review or a recommendation by the DMC, it may be necessary to stop the study before all events have been accrued, and when subjects are still active on the study. In addition, the Sponsor may terminate the study at an investigational site at any time (eg, poorly performing sites, as determined by the number of subjects enrolled or the quality of the study data).

The Investigator and/or Sponsor (or designee) must notify the Institutional Review Board/Independent Ethics Committee (IRB/IEC) of discontinuation of a site or the study and the reason for doing so.

Investigators will be informed by the Sponsor as to when the final study visit is to be completed, and should then schedule all subjects for the End of Study Visit. The window of time for scheduling the visit will be based on a final projection of when the requisite 127 adjudicated events will have been accrued.

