13.1.2. Determination of Sample Size

The target population is subjects who are at higher risk of liver-related clinical complications. Eligible subjects will have a diagnosis of PBC with bilirubin levels $>ULN$ and $\leq 5x ULN$ and/or $ALP > 3 \times ULN$. The following assumptions were used in sample size calculations:

- Exponential survival curves, placebo survival estimate of 0.6 at 8 years with a hazard ratio of 0.60, and total study duration of 10 years (from first subject enrolled), allowing for 4 years of subject accrual and 6 years of follow up.
- Subjects will be randomized in a 1:1 ratio to placebo or OCA.
- The 2 groups will be compared using a 2-sided log rank test at the 5% level of significance.
- Two interim analyses and one final analysis are planned. The first interim analysis will be performed when 50% of the target events are accrued and the second interim will be performed when 75% of the target events are accrued.
- A dropout rate of 10% is assumed

Based on the randomization ratio, significance level, and assumed hazard ratio, a total of 127 events (both groups combined) will provide 80% power to demonstrate a statistically significant difference between OCA and placebo on time to liver-related outcomes, including all-cause mortality.

In addition, based on the remaining assumptions stated above, it is estimated that approximately 428 subjects will be enrolled to attain 127 events.

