13.1.6. Exploratory Efficacy Analyses

13.1.6.1. Responder Analyses

The percentage of subjects with a decrease in ALP of $\geq 15\%$ and $\geq 40\%$ from Baseline will be summarized by treatment group. In addition, the percentage of subjects with ALP \leq ULN will be summarized by treatment group.

The percentage of subjects that meet the criteria of a responder based on each of the definitions below will be summarized by treatment group. The response classification at baseline will also be included in the summary:

- ALP $\leq 3x$ ULN and AST $\leq 2x$ ULN and total bilirubin \leq ULN ([Corpechot 2008](#))
- ALP $\leq 1.5x$ ULN and AST $\leq 1.5x$ ULN and total bilirubin \leq ULN ([Corpechot 2011](#))
- ALP $\leq 1.67x$ ULN and total bilirubin \leq ULN ([Momah 2012](#))
- Normal bilirubin (values \leq ULN) and normal albumin (values \geq lower limit of normal) ([Kuiper 2009](#))
- ALP $\leq 1.76x$ ULN ([Kumagi 2010](#))

Responder analyses will compare treatment groups using a Cochran–Mantel–Haenszel test stratified by the randomization stratification factor. Missing values will be considered as a non-responder.

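### The missing-equals-non-responder rule has no exemption for visits not yet due at study closure, which would dilute any exploratory response rate reported at a fixed timepoint beyond minimum follow-up (minor)

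*Protocol*

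**What the plan says.** Section 13.1.9.3 (Responder Endpoints) fixes the main rule: "any subject who does not provide an assessment at the specified timepoint for the defining of response will be considered to be a non-responder". It spells out the consequence for the percentage: "the subject will be included in the denominator and will not contribute to the numerator". Section 13.1.6.1 (Responder Analyses) states the same without distinguishing reasons: "Missing values will be considered as a non-responder". Section 13.1.9.3 adds an observed-case sensitivity analysis in which "subjects who do not provide an assessment at the specified timepoint for the defining of response will not be included".

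Section 13.1.6.1 sits under the exploratory efficacy analyses. It says that "The percentage of subjects that meet the criteria of a responder based on each of the definitions below will be summarized by treatment group" and gives no timepoint.

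The design facts that matter are these:
- Section 13.1.2 assumes a 10-year study, "allowing for 4 years of subject accrual and 6 years of follow up".
- Section 7.1.3 makes the duration depend on about 127 primary events and expects minimum follow-up of about 6 years.
- Section 13.1.12 plans looks at 64 and 96 events with possible cessation for efficacy.
- Section 7.8 accepts that "it may be necessary to stop the study before all events have been accrued, and when subjects are still active on the study", and has all subjects scheduled for an End of Study visit at closure.

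**The concern.** A missing value can arise because the subject died or left, or because the study closed before the visit was due. Counting the first as failure is a reasonable conservative choice. Counting the second as failure only records the date of entry. The rule as worded does both.

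The protocol treats closure sensibly elsewhere. Time-to-event endpoints are censored at last contact (13.1.9.1), and the ANCOVA endpoints use observed cases as the main analysis (13.1.9.2). Only the responder rule turns closure into failure. If a response rate were tabulated at a late fixed visit, absolute rates would be understated in both arms, the risk difference would be pulled toward zero, and response would look less durable than it was.

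**Working it through.** **Inputs from section 13.1.2.** Placebo survival 0.6 at 8 years, hazard ratio 0.60, 1:1 allocation, 4 years of accrual, closure at 10 years, 10% dropout, 127 events, about 428 subjects. Uniform accrual is my assumption; the protocol does not state the accrual pattern.

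**Reproducing the plan's figures.**
- Events: Freedman's formula gives 16 × 7.849 = 125.6. Lan-DeMets O'Brien-Fleming looks at 50% and 75% inflate this by 1.0196 to 128.0, close to 127.
- Hazards: placebo −ln(0.6)/8 = 0.0639 per year; OCA 0.6 × 0.0639 = 0.0383 per year.
- Event probability by closure T: 1 − [exp(−λ(T−4)) − exp(−λT)]/(4λ). At T = 10 this is 0.398 (placebo) and 0.263 (OCA), mean 0.331.
- Subjects: 127/0.331 gives 383.9 (unrounded inputs), and 383.9/0.9 = 426.6, against about 428 stated.

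**Closure times.** With 10% dropout taken off the sample (428 × 0.9 = 385 effective subjects), 64, 96 and 127 events arrive at about 5.6, 7.7 and 10.0 years. With no dropout they arrive at about 5.2, 7.1 and 9.0 years. Minimum follow-up is closure minus 4 years: about 1.2 to 1.6 years at 64 events, 3.1 to 3.7 at 96, and 5 to 6 at 127.

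**Share of subjects who can reach the Year t visit:** q(t) = min(1, (T − t)/4).

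| Closure T | Share whose visit is not yet due, 1 − q |
|---|---|
| 10.0 (planned) | 0% through Year 6; 25%, 50%, 75% at Years 7, 8, 9 |
| 9.0 (127 events, no dropout) | 25%, 50%, 75% at Years 6, 7, 8 |
| 7.7 (stop at 96 events) | 7.5%, 32.5%, 57.5% at Years 4, 5, 6 |
| 5.6 (stop at 64 events) | 10%, 35%, 60%, 85% at Years 2, 3, 4, 5 |

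For example, at T = 5.6 and Year 3, q = (5.6 − 3)/4 = 0.65, so 35% are not yet due.

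**Effect on the reported result.** Let p be the response rate among subjects due for the visit, with dropout counted as failure, and suppose it does not depend on entry date. The rule then reports p × q in each arm, a difference of (p1 − p0) × q, and a ratio of p1/p0. With assumed rates of 50% and 10% (not in the protocol) and closure at Year 10:
- through Year 6: difference 40 points, ratio 5
- Year 7: 37.5% vs 7.5%, difference 30 points, ratio 5
- Year 8: 25% vs 5%, difference 20 points, ratio 5
- Year 9: 12.5% vs 2.5%, difference 10 points, ratio 5

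**Effect on power.** With assumed rates of 30% and 20% and 214 per arm, power is 66.7% at Year 6. At Year 8 it is 34.6% under the rule and 39.3% if subjects not yet due are excluded. Most of the fall is follow-up that does not exist, which no denominator rule restores.

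**The case against.** The strongest reply is that the document plans no affected analysis. A reader might infer that the trial will report late response rates declining toward zero, or that its treatment effect is understated. The text does not support either inference. Section 13.1.6.1 names no timepoint and no by-year display, and section 13.1.9.3 refers only to a specified one. The timepoint may properly be set in the SAP, so leaving it open is no fault of the protocol. On the planned 4 + 6 year schedule, any timepoint up to about Year 6 loses nobody to closure. Nor would a response defined at each subject's own End of Study visit.

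Other parts of the reply also stand. Responder analyses are exploratory and outside the hierarchy in section 13.1.10. The key secondary ALP and bilirubin analyses use observed cases and are untouched. Entry date is independent of arm, so the dilution is equal in expectation. The early-year figures require an efficacy stop at the first look, where the re-derived boundary is strict (z of about 2.96).

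The observed-case sensitivity analysis answers only part of the point. It removes the subjects not yet due, but it also removes genuine dropouts, whom the main rule deliberately counts as failures. Neither planned analysis gives response among subjects due for the visit with dropout as failure.

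**Conclusion.** The point holds conditionally, at minor severity. The wording of sections 13.1.6.1 and 13.1.9.3 is universal, and following it literally scores visits that fall after closure as failures. If an exploratory response rate is reported at a fixed timepoint beyond minimum follow-up, each arm's rate and the absolute difference are multiplied by q, which is one half at Year 8 for closure at Year 10. The threshold is about Year 6 on the planned schedule. It moves to Year 5 if 127 events arrive by Year 9, and earlier still after an efficacy stop.

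The sizes rest on uniform accrual, the plan's own event-rate assumptions, and response that does not vary with entry date. The response rates used are illustrations only. The ratio of rates and the type I error are not affected, and no primary or key secondary conclusion is at risk.

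**What to change.** Add one sentence to section 13.1.9.3, or to the SAP, and align section 13.1.6.1 with it:
- Apply missing = non-responder only to visits whose window closed on or before the study closure or data cut-off date.
- Remove subjects not yet due at that date from numerator and denominator.
- Keep subjects who died or dropped out as non-responders if their visit would have come due by that date, and remove them if it would not. The denominator then depends only on entry date, which is independent of treatment.
- Keep the observed-case analysis as the sensitivity analysis.

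The cost is smaller denominators at late visits (about half the subjects at Year 8 on the planned schedule with uniform accrual), which should be shown beside each percentage. No data collection, sample size or testing procedure changes.

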13.1.10. Multiple Comparisons/Multiplicity

The key secondary efficacy endpoints are as follows:

- Time to MELD score ≥ 15
- Time to first occurrence of liver transplant or death (all-cause)
- Change from Baseline in total bilirubin at end of study
- Change from Baseline in ALP at end of study

The hypothesis testing of key secondary analyses will compare placebo and OCA and will be conducted in a sequential closed testing gate-keeping procedure (in the order in which the key secondary endpoints are stated above), provided that the primary efficacy endpoint comparison is statistically significant in favor of OCA. If the primary comparison is not statistically significant then comparison of the secondary endpoints will be considered as descriptive and exploratory.

This procedure controls the study-wise type I error.

- First (step 1) placebo and OCA will be compared with respect to the primary efficacy endpoint. If the comparison achieves statistical significance at 2-sided 0.05 level in favor of OCA group, then
- The time to MELD score ≥ 15 will be compared between placebo and OCA (step 2). If the comparison achieves statistical significance at 2-sided 0.05 level in favor of OCA group, then
- The time to liver transplant or death (all-cause) will be compared between placebo and OCA (step 3). If the comparison achieves statistical significance at 2-sided 0.05 level in favor of OCA group, then
- Change from Baseline in total bilirubin will be compared between placebo and OCA (step 4). If the comparison achieves statistical significance at 2-sided 0.05 level in favor of OCA group, then
- Change from Baseline in ALP at the end of study will be compared between placebo and OCA (step 5).

If at any step defined above the comparison is not statistically significant at the 2-sided 0.05 level then the remaining comparisons in the stated hierarchy will be considered descriptive and exploratory. The study-wise type I error will be maintained with the above closed procedure.

Additional efficacy endpoints will be analyzed; however, hypothesis tests will be applied for descriptive and exploratory purposes only.

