KM estimates of the distribution of the time-to-event will be tabulated and graphed by treatment group. The tabulation will include the KM estimate of the medians and corresponding 95% CIs if the medians can be estimated. The number and percent of subjects censored and with events will be presented. The hazard ratio and 95% CI will be determined based on a Cox regression model stratified by randomization strata to estimate the magnitude of the effect.

Sensitivity analyses will be conducted limiting to the separate individual historical control databases, ie, UK-PBC Group and Global PBC Study Group. To evaluate the robustness of the propensity score estimations, additional algorithms and factors may be considered.

Although the study is designed as a placebo-controlled study, the DMC may recommend changes to study conduct based on the pre-specified interim analyses (see [Section 13.1.12](#)), including the potential use of a revised primary efficacy analysis. This analysis would compare all subjects in the OCA population, to all control subjects (randomized placebo and historical controls) on time to liver transplant or death (all-cause), using similar statistical methodology as specified above.

Notably, the planned primary analysis would not be revised without prior agreement with regulatory authorities.

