13.1.12. Continuous Monitoring and Interim Analyses

Blinded safety reports including the accrual of events, drop outs, and/or loss of subjects to commercially available OCA will be reviewed by the DMC on a regular basis.

Two planned interim analyses of the liver-related outcomes will be conducted using the Lan-DeMets O'Brien-Fleming boundaries ([Reboussin 2000](#)). Both interim analyses will be pre-specified and will occur after accrual of 50% (64 events) and 75% (96 events) of clinical outcome events, respectively.

The DMC will review the available efficacy data in conjunction with detailed safety data and other relevant information to recommend continuation, modification, or cessation (for efficacy)

of the study beyond each interim analysis. Modification of the study would not take place without prior agreement with regulatory authorities.

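### Section 13.1.10 claims study-wise type I error control from the closed procedure alone, at 0.05 per step, without accounting for the two efficacy interims; the key secondaries are uncontrolled on either reading of that 0.05

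*Protocol*

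**What the plan says.** - **Level and claim.** Section 13.1.2 sizes the trial with "The 2 groups will be compared using a 2-sided log rank test at the 5% level of significance", next to two interim analyses and one final analysis. Section 13.1.10 puts the primary at step 1 and four key secondaries at steps 2 to 5: time to MELD of 15 or more, time to transplant or death, change in bilirubin, and change in ALP. Each gate reads "If the comparison achieves statistical significance at 2-sided 0.05 level in favor of OCA group, then" on to the next. The section concludes: "The study-wise type I error will be maintained with the above closed procedure". It does not mention the interim analyses.
- **Interims.** Section 13.1.12 states: "Two planned interim analyses of the liver-related outcomes will be conducted using the Lan-DeMets O'Brien-Fleming boundaries". They "will occur after accrual of 50% (64 events) and 75% (96 events) of clinical outcome events", and the data monitoring committee may recommend stopping for efficacy. No overall alpha, nominal level per look or rule for the secondaries is given there.
- **Change of primary.** Section 13.1.8 lets the committee recommend changes on the basis of the interims, "including the potential use of a revised primary efficacy analysis": transplant or death, OCA against placebo and historical controls pooled. Regulators must agree beforehand.

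**The concern.** A fixed testing sequence protects against testing several endpoints. It does not protect against testing at several times. With efficacy looks at 64 and 96 events, a claim of study-wise control also needs a rule for the level at each look, for the primary and for every endpoint tested after it. Section 13.1.10 supplies only the sequence and credits it with the whole of the error control.

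The confirmatory claims on the primary and on the four ordered secondaries rest on that statement. The gap would matter in practice, because under the design assumptions the trial is more likely than not to cross at an interim. A rule chosen after the first unblinded look would be open to challenge as data-driven.

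**Working it through.** **Inputs.** Sections 13.1.2 and 13.1.12: 2-sided 0.05, HR 0.60, 1:1 allocation, 127 events, 80% power, looks at 64, 96 and 127 events. Information fractions are 64/127 = 0.504, 96/127 = 0.756 and 1.

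**1. The plan's own figures.** Schoenfeld for a fixed design: 4(1.960 + 0.842)² / (ln 0.60)² = 120.3, so 121 events. The group-sequential inflation is 1.020, giving 123; Freedman's fixed-design count is 126. Power at 127 events with the adjusted boundaries is 81.3%. For N, the average event probability is 0.331 (exponential survival, 4 years' accrual, 10 years in total): 127/0.331 = 384, and 384/0.90 = 427 against the stated 428. The 127 and 428 are not in error.

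**2. Boundaries.** The O'Brien-Fleming-type spending function at 0.025 per side is 2[1 − Φ(2.241/√t)]. Cumulative spend is 0.00159, 0.00994 and 0.02500. Solving for the critical values:

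| Events | z | 2-sided p |
|---|---|---|
| 64 | 2.949 | 0.0032 |
| 96 | 2.348 | 0.0189 |
| 127 | 2.016 | 0.0438 |

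**3. Primary.** With these interim boundaries and a final z of 1.960, as 13.1.10 literally reads, the overall 2-sided error is 0.0555. With a final z of 2.016 it is 0.0500.

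**4. Chance of an early crossing.** At HR 0.60 the drift is 0.5108 × √127 / 2 = 2.878. The probabilities of first crossing at the three looks are 0.182, 0.383 and 0.248. The interim share is 0.182 + 0.383 = 0.565, about 57%.

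**5. Key secondary at a flat 0.05.** Suppose the primary effect is real, the secondary is null, the primary uses the correct boundaries, and the secondary is tested at z = 1.960 at whichever look the primary crosses. The one-sided error is the sum over looks k of P(primary first crosses at k and secondary Z at k > 1.960). The correlation is assumed.

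| Correlation with primary | Worst case over the primary's effect | At HR 0.60 |
|---|---|---|
| 0.5 | 2.8% | 2.8% |
| 0.7 | 3.0% | 2.9% |
| 0.9 | 3.4% | 2.8% |

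The target is 2.5%. The worst case falls near HR 0.61 at correlation 0.5, 0.69 at 0.7 and 0.78 at 0.9. Using 0.05 at the primary's final look barely changes these figures.

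**6. Change of primary.** The documents state no switching criterion, no correlation between the two tests and no bound on bias from the historical controls. No error rate can be computed without inventing all three.

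**The case against.** **On the primary.** Section 13.1.12 names a spending function, and that fixes the final critical value as well as the interim ones. Section 13.1.2 lists the 5% level beside the three analyses, so 0.05 can fairly be read as the overall level, and 127 events give the stated power with the adjusted boundary. Nominal levels per look are ordinary SAP content, and section 13 requires the SAP to be approved before the first interim. This largely stands. A reader might infer from 13.1.10 that the trial's error rate simply exceeds 5%. For the primary that is true only if 13.1.10 overrides 13.1.12, and then by about half a point. What remains is that 13.1.10 neither says its 0.05 is the overall level nor refers to 13.1.12.

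**On the secondaries.** The protocol never says they are tested at an interim, the correlations are assumed, and the worst case is not at the design hazard ratio. All true, which is why a range and the HR 0.60 figures are given. But 13.1.10 opens the gate whenever the primary is significant, and 13.1.12 allows stopping for efficacy, so testing at an early stop is what the text provides for. Steps 2 and 3 are built from components of the primary composite, so a positive correlation is plausible.

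**On the change of primary.** It is only a possible recommendation and needs prior regulatory agreement. That limits the risk but is governance, not error control. A reader might also see a contradiction with section 5.5.2.3, which keeps the historical and placebo comparisons separate. That section describes the planned supportive analyses, whereas 13.1.8 describes a departure from plan, so the tension is soft.

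**Conclusion.** The claim of study-wise control in 13.1.10 is unsupported as written.

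- **Primary:** an inconsistency to reconcile. Overall 2-sided error is 5.55% on the literal reading and 5.00% if 0.05 is the level being spent.
- **Key secondaries:** a real gap on either reading. One-sided error is about 2.8% to 3.4% at worst and 2.8% to 2.9% at HR 0.60, against 2.5%, for assumed correlations of 0.5 to 0.9. The excess is modest, but the route to it is likely to be used (about 57% at HR 0.60).
- **Revised primary:** no error-control rule is given for a change made after unblinded efficacy looks. A reader might want a figure for the inflation; the documents do not support one.

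**What to change.** 1. **Section 13.1.10, primary.** State that 0.05 is the overall 2-sided level and that the primary is judged against the 13.1.12 spending boundaries: 2-sided p about 0.0032, 0.0189 and 0.0438 at 64, 96 and 127 events, recomputed at the actual information.
2. **Section 13.1.10, secondaries.** State that the two time-to-event key secondaries are tested in order at the analysis where the primary crosses, each against its own pre-specified alpha-spending boundary. Under its null, each then crosses at any look with one-sided probability at most 0.025, whatever the correlation. Bilirubin and ALP are end-of-study ANCOVA endpoints with no event-based information, so give them a pre-specified conservative level at an early stop.
3. **Section 13.1.8.** State that the randomised OCA-versus-placebo log-rank test stays the confirmatory primary after any unblinded interim, and that the pooled placebo-plus-historical comparison is supportive only.

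**Cost.** Protocol and SAP wording, in place before the first interim, with slightly stricter nominal levels. Power for the primary at 127 events is 81.3% with the correct boundaries, so no extra events or patients are needed.
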